3.4.3 Biomarker data

The relationship of programmed cell death ligand 1 (PD-L1) expression and, if applicable, of exploratory biomarkers to clinical outcomes (including but not restricted to) of PFS, OS, ORR, and DoR may be presented.

PD-L1 expression determined by immunohistochemistry (IHC) will be reported in the CSR.

Remaining exploratory analysis described in the CSP may be reported outside the main CSR, including (and not limited to) the following exploratory endpoints as specified in CSP section 3:

- Blood **CCI** relative to efficacy outcomes (OS, PFS, and ORR)
- Biomarker analysis of blood and tissue to assess exploratory markers
- Biomarker status before and after treatment and durvalumab PK exposure and relationship with clinical outcomes, efficacy, AEs and/or safety parameters, as deemed appropriate
- Correlation of biomarkers with response to durvalumab treatment and/or the progression of cancer

A separate SAP for the remaining exploratory analysis as above will be prepared where necessary.

3.5 Exploratory variables

3.5.1 Calculation or derivation of patient-reported health state utility (EQ-5D-5L)

The health state utility will be assessed using the EQ-5D-5L index ([EuroQoL 2013](#)). The EQ-5D is a standardised measure of health status developed by the EuroQol Group in order to provide a simple, generic measure of health for clinical and economic appraisal. Applicable to a wide range of health conditions and treatments, it provides a simple descriptive profile and a single index value for health status that can be used in the clinical and economic evaluation of health care.

The index comprises of 5 dimensions of health (mobility, self-care, usual activities, pain/discomfort, and anxiety/depression) ([EuroQoL 2013](#)). For each dimension, respondents select which statement best describes their health on that day from a possible 5 options of increasing levels of severity (no problems, slight problems, moderate problems, severe problems, and extreme problems). A unique EQ- 5D health state is referred to by a 5-digit code, allowing for a total of 3125 health states. For example, state 11111 indicates no problems on any of the 5 dimensions. These data will be converted into a weighted health state index by applying scores from EQ-5D value sets elicited from general population samples (the base case will be the United Kingdom valuation set, with other country value sets applied in scenario analyses). Where value sets are not available, the EQ-5D-5L to EQ-5D-3L crosswalk will be applied ([Oemar and Janseen 2013](#)). Change from baseline in utility scores will be evaluated. In addition to the descriptive system, respondents also assess their health on the day of assessment on a visual analogue scale, ranging from 0 (worst imaginable health) to 100 (best imaginable health). This score is reported separately.

3.5.2 Health care resource use

To investigate the impact of treatment and disease on health care resource, the following exploratory variables may be captured:

- Planned and unplanned hospital attendances beyond trial protocol mandated visits (including physician visits, emergency room visits, day cases and admissions).
- Primary sign or symptom for hospital/inpatient/emergency room visit
- Length of hospital stay
- Planned and unplanned hospital attendances beyond trial protocol mandated visits (including physician visits, emergency room visits, day cases and admissions)
- Primary sign or symptom for hospital/inpatient/emergency room visit
- Length of hospital stay
- Length of any time spent in an intensive care unit (ICU)

Where admitted overnight, the length of hospital stay will be calculated as the difference between the date of hospital discharge (or death date) and the start date of hospitalisation or start of study drug if the start of study drug is after start date of hospitalisation (length of hospital stay = end date of hospitalisation – start date of hospitalisation + 1). Patients with missing discharge dates will be calculated as the difference between the last day with available data and the start date of hospitalisation. The length of ICU stay will be calculated using the same method.

3.5.3 Collection of data due to COVID-19

Due to COVID-19 pandemic, two eCRF pages were added to collect details on visits impacted (eCRF page [VISITP]) and concomitant medications not started (eCRF page [CMNSP]). More details were provided in the eCRF completion guidelines (v06, 27Apr2021) for those new pages and for other pages.

4 ANALYSIS METHODS

There will be 1 treatment comparison of interest:

- Durvalumab (MEDI4736) 1500mg vs placebo

Formal statistical analyses will be performed to test the main hypothesis:

- H0: No difference between durvalumab and placebo
- H1: Difference between durvalumab and placebo

The primary endpoint is PFS as assessed by BICR. The study has been sized to characterise the PFS benefit of durvalumab relative to placebo.

Results of all statistical analyses will be presented using a 95% confidence interval (CI) and 2-sided p-value, unless otherwise stated.

4.1 General principles

Efficacy and PRO data will be summarised and analysed on the mITT set. PK data will be summarised on the PK analysis set. Safety and treatment exposure will be summarised based upon the safety analysis set, except deaths that will be analysed on the ITT set.

Immunogenicity data will be summarised on the ADA analysis set. Study population and demography data will be summarised based upon the mITT set.

Selected analyses based on the mITT set will be repeated on the ITT set. For supporting listings, those will be produced on ITT and mITT patients will be identified.”

All data collected will be presented in data listings by treatment group and subject number. All summaries will be presented by treatment group, unless otherwise specified.

A year is defined to be 365.25 days and a month is defined to be 30.4375 days.

The below mentioned general principles will be followed throughout the study:

- Descriptive statistics will be used for all variables, as appropriate, and will be presented by treatment arm. Continuous variables will be summarised by the number of observations, mean, standard deviation, median, upper and lower quartiles, minimum, and maximum. For log transformed data it is more appropriate to present geometric mean, coefficient of variation (CV), median, minimum and maximum. Categorical variables will be summarised by frequency counts and percentages for each category.
- Unless otherwise stated, percentages will be calculated out of the population total and for each treatment arm.
- For continuous data, the mean and median will be rounded to 1 additional decimal place compared to the original data and rounded up (i.e., if original data is provided to 1 decimal place, a mean of 2.425 will become 2.43). The standard deviation will be rounded to 2 additional decimal places compared to the original data. Minimum and maximum will be displayed with the same accuracy as the original data.
- For categorical data, percentages will be rounded to 1 decimal place.
- Results of all statistical analysis will be presented using a 95% CI and 2-sided p-value, unless otherwise stated.
- P-values will be rounded to 3 decimal places. P-values less than 0.0005 (e.g. 0.0002) will not be rounded to 3 decimal places (e.g. 0.000) but instead be displayed as <0.001. P-values output as <0.0001 by statistical software will not be rounded and displayed in the same way ('<0.0001').
- SAS® Enterprise Guide (EG) will be used for all analyses.

4.1.1 Baseline

In general, for efficacy and PRO endpoints the last observed measurement prior to or on the date of randomisation will be considered the baseline measurement. However, for PRO endpoints if an evaluable assessment is only available after randomisation but before the first dose of randomised treatment then this assessment will be used as baseline. For safety endpoints, the last observation before the first dose of IP will be considered the baseline measurement unless otherwise specified. For assessments on the day of first dose where time is not captured, a nominal pre-dose indicator, if available, will serve as sufficient evidence that the assessment occurred prior to first dose.

Assessments on the day of the first dose where neither time nor a nominal pre-dose indicator are captured will be considered prior to the first dose if such procedures are required by the CSP to be conducted before the first dose.

In all summaries change from baseline variables will be calculated as the post-treatment value minus the value at baseline. The % change from baseline will be calculated as (post-baseline value - baseline value) / baseline value x 100.

4.1.2 Methods for multiplicity control

The multiple testing procedure, as shown in Figure 2, will define which significance levels should be applied to the interpretation of the raw p-values for the primary endpoint of PFS [REDACTED]

[figure not shown]
There will be up to [REDACTED] DCOs timepoints in the study. The DCO for the final (primary) PFS analysis (first analysis) on the mITT will be done when reaching approximately [REDACTED] BICR PFS events or approximately [REDACTED] months follow-up post last participant randomization, whichever occurs first, and the first OS interim analysis on the [REDACTED] will be conducted at the same time (with approximately [REDACTED] OS events, [REDACTED] maturity). The DCO for the second interim OS analysis on the mITT will be performed at approximately [REDACTED] months after the OS first interim analysis (approximately [REDACTED] OS events in the mITT with [REDACTED] maturity), which may be removed as specified in section 1.3. The DCO for the final OS analysis on the mITT will be performed when reaching approximately [REDACTED] OS events ([REDACTED] maturity) or approximately [REDACTED] months follow-up from the last participant randomization, whichever occurs first.

The overall 5% type 1 error will be allocated to the PFS analysis. The 5% alpha level allocated to the OS analyses will be controlled at the interim and final timepoints by using the Lan DeMets (Lan and DeMets 1983) spending function that approximates an O'Brien Fleming approach, where the significance level applied at the interim depends upon the proportion of information available. If [REDACTED] or [REDACTED] of the OS events required at the time of the final OS analysis is available at the time of the interim analysis (i.e. [REDACTED] or [REDACTED] OS events have occurred), the 2-sided significance level to be applied for the OS interim analysis would be [REDACTED] and [REDACTED] respectively, and the 2-sided significance level to be applied for the final OS analysis would be [REDACTED]. Note that the actual allocation of alpha across the three analysis times will be driven by the actual information fraction associated with the analysis and alpha allocation for OS first interim analysis will assume that the OS second interim and final analysis will take place. If second interim analysis is removed after the first interim analysis is complete, the alpha has been spent for first interim analysis will not be changed, the remaining alpha will be calculated based on actual information fraction

and allocated for OS final analysis (i.e. The alpha level allocated to the OS first interim analyses and final analysis would be [CCI] and [CCI] respectively if removing the OS second interim analysis).

If the null hypothesis is rejected for either [CCI] interim or final analyses, 5% alpha level will be further recycled to the [CCI] analysis. To control the type I error rate, the DCO for the [CCI] analysis will be fixed at the same time as that of the [CCI] analysis and approximately [CCI] BICR PFS events are expected in the ITT population at this time.

If the null hypothesis is rejected for the [CCI] analysis, [CCI] alpha level will be finally recycled to [CCI] analysis. The [CCI] alpha level will be controlled at the interim and final analyses by using the Lan DeMets method described as above. At the time of interim and final analyses (same time as the [CCI] analysis), the number of [CCI] events is expected to be approximately [CCI] maturity), and [CCI] maturity), respectively, which corresponds to an information fraction of approximately [CCI] and [CCI] at each analysis, the resulting alpha was calculated to be [CCI] and [CCI] at subsequent analyses. The alpha allocation for OS interim and final analysis in the ITT population will follow the same rule and consideration above for the analysis in the mITT population.

4.1.3 Visit window for safety and PRO assessments

Time windows will need defining for any presentations that summarise values by visit. The following conventions should also apply:

- The time windows should be exhaustive so that data recorded at any time point has the potential to be summarised. Inclusion within the time window should be based on the actual date and not the intended date of the visit.
- All unscheduled visit data and repeated measurements should have the potential to be included in the summaries. This data should take into account the definition of windows per visits described in the point below.
- The window for the visits following baseline will be constructed in such a way that the upper limit of the interval falls half way between the two visits (the lower limit of the first post-baseline visit will be Day 2). If an even number of days exists between two consecutive visits, then the upper limit will be taken as the midpoint value minus 1 day.

For example, the visit windows for vital signs data are:

- Day 29, visit window 2 – 42
 - Day 57, visit window 43 – 70
 - Day 85, visit window 71 – 98
 - Day 113, visit window 99 – 126
- For summaries showing the maximum or minimum values, the maximum/minimum value recorded on-treatment will be used (regardless of where it falls in an interval).
 - Listings should display all values contributing to a time point for a patient.
 - For visit based summaries:
 - If there is more than one value per patient within a time window then the closest value to the scheduled visit date should be used, or the earlier in the event the values are equidistant from the nominal visit date. If there are two values recorded on the same day and the parameter is CTCAE gradable then the record with the highest toxicity grade should be used. Alternatively, if there are two records recorded on the same day and the toxicity grade is the same (or is not calculated for the parameter) then the average of the two records should be used. The listings should highlight the value for that patient that went into the summary table, wherever feasible. Note: in summaries of extreme values all on-treatment values collected are used including those collected at unscheduled visits.
 - To prevent very large tables or plots being produced that contain many cells with meaningless data, for each treatment group visit data should only be summarised if the number of observations is greater than the minimum of 20

and > 1/3 of patients dosed (i.e., randomised and received durvalumab/placebo).

- For summaries at a patient level, all values should be included, regardless of whether they appear in a corresponding visit-based summary, when deriving a patient level statistic such as a maximum.
- Baseline will be defined as the last non-missing measurement prior to the first dose of study treatment. For laboratory data with no time collected, any assessments made on day 1 will be considered pre-dose. If there are two visits equally eligible to assess patient status at baseline (e.g., screening and baseline assessments both on the same date prior to first dose with no washout or other intervention in the screening period) with assessment time missing, the average can be taken as a baseline value. For non-numeric laboratory tests (i.e. some of the urinalysis parameters) where taking an average is not possible then the best value would be taken as baseline as this is the most conservative. In the scenario where there are two assessments on day 1, one with time recorded and the other without time recorded, the one with time recorded would be selected as baseline.

Where safety data are summarised over time, study day will be calculated in relation to date of first treatment.

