8.2.3 Vital signs

Vital signs (blood pressure [BP], pulse, temperature, and respiration rate) will be evaluated according to the SoAs. WT is also recorded at each visit along with vital signs.

First infusion

On the first infusion day, participants will be monitored and vital signs collected/recorded in eCRF prior to, during, and after infusion of IP as presented in the bulleted list below.

BP and pulse will be collected from participants before, during, and after each infusion at the following times (based on a 60-minute infusion):

- Prior to the beginning of the infusion (measured once from approximately 30 minutes before up to 0 minutes [ie, the beginning of the infusion])
- Approximately 30 minutes during the infusion (halfway through infusion)
- At the end of the infusion (approximately 60 minutes ± 5 minutes)

If the infusion takes longer than 60 minutes, then BP and pulse measurements should follow the principles as described above or be taken more frequently if clinically indicated. A 1-hour observation period is recommended after the first infusion of durvalumab.

Subsequent infusions

BP, pulse, and other vital signs should be measured and collected/recorded in the eCRF prior to the start of the infusion. Participants should be carefully monitored, and BP and other vital signs should be measured during and post infusion as per institution standard and as clinically indicated. Any clinically significant changes in vital signs should be entered onto an unscheduled vital signs CRF page.

Situations in which vital signs results should be reported as AEs are described in Section 8.3.7. For any AEs of infusion reactions, the vital signs values should be entered into the CRF.

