8.3.13 Adverse events of special interest

An adverse event of special interest (AESI) is one of scientific and medical interest specific to understanding of the IP and may require close monitoring. An AESI may be serious or non-serious. The rapid reporting of AESIs allows ongoing surveillance of these events in order to characterise and understand them in association with the use of this IP.

AESIs for durvalumab include but are not limited to events with a potential inflammatory or immune-mediated mechanism and which may require more frequent monitoring and/or interventions such as steroids, immunosuppressants, and/or hormone replacement therapy. These AESIs are being closely monitored in clinical studies with durvalumab monotherapy and combination therapy. An imAE is defined as an AESI that is associated with drug exposure and is consistent with an immune-mediated mechanism of action and where there is no clear alternate aetiology. Serologic, immunologic, and histologic (biopsy) data, as appropriate, should be used to support an imAE diagnosis. Appropriate efforts should be made to rule out neoplastic, infectious, metabolic, toxin, or other etiologic causes of the imAE.

If the Investigator has any questions in regards to an event being an imAE, the Investigator should promptly contact the Study Physician.

AESIs/imAEs observed with anti PD-1/PD-L1 agents such as durvalumab include:

- Diarrhoea/colitis and intestinal perforation
- Pneumonitis/ILD
- Endocrinopathies (ie, events of hypophysitis/hypopituitarism, adrenal insufficiency, hyper- and hypo-thyroidism, and type I diabetes mellitus)
- Hepatitis/transaminase increases

- Nephritis/blood creatinine increases
- Pancreatitis/serum lipase and amylase increases
- Rash/dermatitis
- Myocarditis
- Myositis/polymyositis
- Other inflammatory responses that are rare/less frequent with a potential immunemediated aetiology include, but are not limited to, haematological events, neuropathy/neuromuscular toxicity (eg, Guillain-Barré and myasthenia gravis), noninfectious encephalitis, non-infectious meningitis, pericarditis, rheumatological events, sarcoidosis, skin events, uvetitis [and other events involving the eye] and vasculitis.

In addition, infusion-related reactions and hypersensitivity/anaphylactic reactions with a different underlying pharmacological aetiology are also considered AESIs.

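### The SAP's by-visit windows have no place for the Day 1 mid- and end-infusion blood pressure and pulse readings, and no worst-value table for vital signs is planned to pick them up

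*SAP*

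**What the plan says.** **Collection.** For the first infusion, Protocol 8.2.3 has "vital signs collected/recorded in eCRF prior to, during, and after infusion of IP". Blood pressure and pulse are timed before the start, about 30 minutes in, and at the end (about 60 minutes). For later infusions, pre-infusion values are recorded. Measurement during and after the infusion follows institutional standard and clinical need, and clinically significant changes go on an unscheduled page. Values are also to be entered for any infusion-reaction adverse event.

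**Reporting period and windows.** SAP 3.3.4 treats vital signs from the date of first dose to 30 days after last dose as on-treatment, and refers to 4.1.3 for visit windows and multiple records. In 4.1.3, "study day will be calculated in relation to date of first treatment", baseline is the last non-missing value before first dose, and "the lower limit of the first post-baseline visit will be Day 2". The worked vital-signs example begins with "Day 29, visit window 2 – 42". The same section states: "The time windows should be exhaustive so that data recorded at any time point has the potential to be summarised".

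**Several values in a window.** The value closest to the nominal date is used. For two values on the same day, the higher toxicity grade is taken if the parameter is gradable. If the grades are equal or no grade is calculated, "then the average of the two records should be used".

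**Planned output.** SAP 4.2.5.3 plans absolute values and change from baseline at each scheduled measurement by actual treatment group, optional box plots, and a listing.

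**Adverse events.** In Protocol 8.3.13, "infusion-related reactions and hypersensitivity/anaphylactic reactions with a different underlying pharmacological aetiology are also considered AESIs". SAP 3.3.1 lists infusion/hypersensitivity reactions among the categories of special or possible interest, and SAP 4.2.5.1 tabulates these categories by arm.

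**The concern.** The plan collects readings during and just after the first infusion, classes them as on-treatment, and then gives them no slot in the only vital-signs table it commits to. That conflicts with the SAP's own statement that the windows should leave nothing out.

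The gap matters because of Protocol 8.3.7. That section says protocol-mandated vital signs will be summarised in the study report, and on that ground restricts adverse event reporting of vital-sign deterioration to cases that are serious or lead to discontinuation. Accompanying signs and symptoms are still reported. A non-serious, asymptomatic fall in blood pressure or rise in pulse during the first infusion is therefore left to the vital-signs summary, and the windows then omit it. It would appear only in a listing.

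The same-day rule raises a second, conditional issue. On a later infusion day, a value recorded during a reaction may be averaged with the normal pre-infusion value, so the summarised change is smaller than the change that occurred.

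**Working it through.** **1. Reproduce the SAP's windows.** The inputs are nominal Days 29, 57, 85, 113 and 141 (28 days apart), a lower limit of Day 2 for the first window, and the rule "If an even number of days exists between two consecutive visits, then the upper limit will be taken as the midpoint value minus 1 day". Each upper limit is the midpoint of two consecutive nominal days minus 1, and each later lower limit is the previous upper limit plus 1.

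| Nominal day | Midpoint to next | Upper limit | Window |
|---|---|---|---|
| 29 | (29+57)/2 = 43 | 42 | 2–42 |
| 57 | (57+85)/2 = 71 | 70 | 43–70 |
| 85 | (85+113)/2 = 99 | 98 | 71–98 |
| 113 | (113+141)/2 = 127 | 126 | 99–126 |

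All four match SAP 4.1.3. Day 1 is in none of them.

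**2. Place the three timed first-infusion readings.** Study day counts from first treatment, so all three fall on Day 1.

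| Reading (Protocol 8.2.3) | Can be baseline? | In a window? |
|---|---|---|
| Before the start | Yes, it precedes first dose | Not needed |
| About 30 minutes in | No, dosing has begun | No |
| End, about 60 minutes | No | No |

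Two of the three have no by-visit slot. If all of about 400 randomised participants are dosed (an assumption and an upper bound), that is 2 × 400 = 800 blood pressure and 800 pulse readings.

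**3. Look for another planned summary.** SAP 4.1.3 says maximum and minimum summaries use every on-treatment value, including unscheduled ones, but this applies only where such a summary exists. SAP 4.2.5.2 plans shift tables by worst grade for laboratory data, and 4.2.5.4 plans a shift to worst on-treatment evaluation for ECGs. SAP 4.2.5.3 names nothing comparable for vital signs.

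**4. Same-day averaging on later infusion days.** SAP 3.3.2 derives toxicity grades at each visit for laboratory data; 3.3.4 and 4.2.5.3 describe none for vital signs. As written, two same-day vital-sign values are averaged. If one equals the pre-infusion level and the other departs from it by d, the mean departs by d/2. Illustrative falls, not taken from the documents:

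- d = 20 mmHg is summarised as 10 mmHg;
- d = 40 mmHg as 20 mmHg;
- d = 60 mmHg as 30 mmHg.

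This happens only if all of the following hold: a second same-day value exists, no grade is calculated (or the grades are equal), and that day is the one closest to the nominal visit. The rule is written for two records and does not say what to do with three.

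**The case against.** **Infusion reactions are analysed elsewhere.** This is the strongest objection, and it stands. SAP 4.2.5.1 tabulates infusion/hypersensitivity reactions by arm and group term, including serious, grade 3 or 4, causally related, leading to discontinuation, steroid use and fatal outcome. A reader might infer from the window gap that the plan cannot show an infusion effect by arm, or that infusion-reaction information survives only in a listing. The documents do not support that. The loss is confined to vital-sign changes that do not themselves become adverse events.

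**The wording in SAP 4.2.5.3 may already cover Day 1.** That section refers to each scheduled measurement, the protocol schedules the mid- and end-infusion readings, and the windows are given as an example. This reading is possible. But 3.3.4 sends vital signs to 4.1.3, and 4.1.3 provides no slot. At the least, the sections disagree.

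**The values can be recovered.** Patient-level statistics may use all values, and SAP 4.2.5 allows extra safety summaries. Both are true, but both are permissions; no vital-signs table is named.

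**The averaging is conditional.** This also stands. It would not apply where the sponsor graded the parameter and the grades differed, or where another day was closer to nominal. It cannot be stated that later in-reaction readings are generally diluted.

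**Purpose.** Protocol 8.2.3 does not say the first-infusion readings are taken to detect infusion reactions. That is an inference from the monitoring it describes.

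**Conclusion.** The point holds in a limited form. SAP 4.1.3 is inconsistent with its own aim of complete coverage and with SAP 3.3.4: the Day 1 mid- and end-infusion blood pressure and pulse readings are on-treatment, are not baseline, and fall in no window. Without a worst-value table, the plan does not summarise vital-sign changes that Protocol 8.3.7 keeps out of adverse event reporting because the study report is to summarise them.

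The size is two of three timed first-infusion readings per dosed participant. On later infusion days, the summarised excursion is halved where the averaging conditions are met. The reading counts assume that everyone randomised is dosed, and the mmHg figures are illustrative. Neither is an error in a planned estimate.

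It would go too far to say that all first-infusion readings are lost, since the pre-infusion one can serve as baseline, or that infusion reactions go unanalysed. Safety is summarised descriptively and no efficacy analysis is touched. The change is worth making because the data are already collected.

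**What to change.** In SAP 4.1.3 and 4.2.5.3:

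1. Add Day 1 mid-infusion and Day 1 end-of-infusion as summary time points for blood pressure and pulse, with change from the Day 1 pre-infusion value, by arm.
2. Add a by-arm summary of minimum and maximum on-treatment vital signs that includes Day 1 readings after the start of infusion and unscheduled readings.

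The by-visit table could also be restricted to pre-infusion readings, which would remove the averaging question. Do that only together with item 2; alone, it would drop in-reaction values from every summary. State whether any vital sign is graded, and what happens with more than two same-day records.

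Separately, Protocol 8.2.3 refers to each infusion within its first-infusion text, while its later text leaves measurement during and after subsequent infusions to institutional standard. Those two statements should be reconciled so that the expected data are clear.

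The cost is SAP wording and one or two extra descriptive tables from data already in the eCRF.
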